This treatment study, will be able to compare response rate of catatonia to RUL ECT and BL ECT. Also having a control group of catatonia patients, which will not be treated with ECT will provide additional information on early ECT treatment of Katatonia.

Objectives

- Study the response rate of catatonia to right unilateral (RUL) ECT and bilateral (BL) ECT.
- Compare response rate of catatonia to RUL ECT and BL ECT
- Analyze and describe the change of clinical signs and symptoms after ECT treatment series

Methods and Measures

Design

This study is a case control study. Currently ECT is considered standard of treatment for catatonia in addition to alternative medication options.

Study participants meeting inclusion and exclusion criteria will be and providing informed consent will be randomly assigned to receive either bilateral electroconvulsive treatment (BLECT) or right unilateral electroconvulsive treatment (RULECT)

- Patients who are otherwise eligible and consent to participate in our study, but refuse ECT (or ones who are unable to consent but their court appointed legal guardian or health care power of attorney refuse ECT) will be enrolled as a control group. The control group will undergo all the same laboratory investigations and Bush Francis measurements for evaluation of their catatonia but will not receive ECT.
- Informed consent will be obtained from the study participant or their legally authorized representative by the principal investigator or sub-investigator.
- Prior to treatment each patient will be examined by a clinician (psychiatrist and psychiatric resident) in which the following information will be obtained:

- **Psychiatric interview** with uniformed questioner

- **HPI** with onset, course of presenting symptoms, comorbidities, *precipitating illness or life events – emphasis upon psychological stress*

- **Substance abuse screening**

- **Psychiatric history** – Psychiatric diagnoses with age/date of diagnoses

- **Medical history**, with focus on comorbid developments and chronic medical disease states – especially if recent worsening or change in therapy

- **Previous episodes of catatonia** – dates and pertinent developments to social history (as noted above with HPI) with time course and treatment response/failure to ECT or medications

- **Recent medication changes**, with specific focus on timing of symptoms if possible – regimen prior to symptom/sign development, medication changes, and current medication

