Study participants' medical histories, examinations, administration of rating scales (Bush Francis scale, MoCA and Hamilton Depression scale) will be done in the respective patient's room on the adult inpatient psychiatry unit at Wake Forest Baptist Health.

ECT treatments will be administered in OR at Wake Forest Baptist Health.

Subjects selection criteria

- **Inclusion Criteria**
- Adult patients admitted to WFBMC Inpatient Psychiatry unit with catatonia who are clinically eligible for ECT.
- Clinical catatonia as evidenced by a Bush-Francis Catatonia Rating Scale (BFCRS) score of 4 or more

- **Exclusion Criteria**

Pregnant women

Patients with any of the following medical conditions which are contraindications for ECT:

- Pheochromocytoma
- History of stroke within the past 3 months
- Cardiac conduction defects
- Cerebral or aortic aneurysms

- **Sample Size**

This study will require 30 or more to answer the questions stated in the study objectives. We will enroll 15 ECT subjects and 15 control group subjects (total sample size 30).

Interventions and Interactions

- Participants will be administered the Bush Francis Scale (BFCRS) by the principal investigator or the study coordinator the day before each ECT procedure and the day after each ECT procedure.
- Participants will receive up to 10 ECT treatments. These ECT treatments can be terminated earlier if study participants show objective clinical improvement defined as a reduction of 50% or more in the Bush Francis scale score

Outcome Measure(s)

Reduction of 50% or more in the Bush- Francis Scale (BFCRS) score.

Analytical Plan

Results will be analyzed initially using descriptive statistics. Comparison between groups will be done using chi square tests for proportions, t-tests, ANOVA procedures or other appropriate statistical analytical procedures. Regression analysis may be performed to identify independent outcome predictors. Other inferential statistical analysis will be conducted as appropriate.

Human Subjects Protection

Subject Recruitment Methods

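### The stated size of 30 is presented as enough to answer the objectives, but the only comparative one (RUL vs BL) rests on 15 ECT patients, too few for any but very large differences

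*Combined protocol and SAP*

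**What the plan says.** Under Sample Size (in Subjects selection criteria) the protocol states: "This study will require 30 or more to answer the questions stated in the study objectives". It continues: "We will enroll 15 ECT subjects and 15 control group subjects (total sample size 30". No significance level, power, expected response rate, detectable difference or dropout allowance is given there or elsewhere.

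The end of Background, Rationale and Context says the study "will be able to compare response rate of catatonia to RUL ECT and BL ECT", and that an untreated control group "will provide additional information on early ECT treatment of Katatonia".

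Objectives lists three items: to study the response rate to RUL and BL ECT, to "compare response rate of catatonia to RUL ECT and BL ECT", and to "Analyze and describe the change of clinical signs and symptoms after ECT treatment series". Only the second compares groups.

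Under Methods and Measures, Design, eligible consenting patients are "randomly assigned to receive either bilateral electroconvulsive treatment (BLECT) or right unilateral electroconvulsive treatment (RULECT"; no ratio is given. The controls are "Patients who are otherwise eligible and consent to participate in our study, but refuse ECT", or patients whose guardian or health care agent refuses it. They have the same laboratory tests and Bush-Francis (BFCRS) measurements but no ECT.

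The outcome is binary: a fall of at least half in the BFCRS score. The Analytical Plan begins with descriptive statistics, then names chi-square tests for proportions, t-tests, ANOVA and other suitable procedures for comparing groups.

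**The concern.** The total of 30 is offered as what the objectives need, yet half of those patients do not contribute to the objective that compares two treatments. A reader who sees 30 alongside a promise to compare RUL with BL will take the comparison to be adequately sized. The comparison actually has about seven or eight patients per arm.

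The risk lies in how the result is read. With arms this small, a non-significant chi-square test is the likely outcome even if the placements differ substantially. The plan does not call the comparison exploratory, does not specify a confidence interval for the difference, and does not say how a non-significant result will be interpreted. Nothing in it prevents such a result from being reported as similar efficacy of two active treatments.

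**Working it through.** **The plan's own figure.** The 30 can be neither reproduced nor refuted, because the documents give none of the inputs to a calculation. The check is therefore what the stated design can deliver for RUL vs BL.

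**Inputs from the protocol.** 15 ECT patients (Sample Size); random assignment to RUL or BL (Design); binary response (Outcome Measure(s)); chi-square test, version not specified (Analytical Plan).

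**Assumptions, not in the documents.** 1:1 allocation, hence 7 vs 8; two-sided 5%; no dropout. The last is favourable, since Informed Consent lets consent to ECT be withdrawn at any time. As the chi-square version is open, three tests are shown.

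**Method.** Power = Σ P(X₁=a)·P(X₂=b) over all outcomes (a, b) with p ≤ 0.05, where X₁ ~ Bin(n₁, p₁) and X₂ ~ Bin(n₂, p₂). For a fixed difference d, p₁ runs from d to 1 with p₂ = p₁ − d, and both orders (8 vs 7, 7 vs 8) are taken.

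**Results: lowest to highest power over all rate pairs.**

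| True difference | Uncorrected chi-square | Fisher | Yates |
|---|---|---|---|
| 50 points | 47.7–77.3% | 36.3–50.0% | 22.7–36.3% |
| 30 points | 18.6–35.3% | 5.8–18.1% | 2.9–9.1% |

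The smallest chance of missing a 30-point difference is 100 − 35.3 = 64.7% (uncorrected), 100 − 18.1 = 81.9% (Fisher) or 100 − 9.1 = 90.9% (Yates).

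**Check by hand at the boundary.** Suppose all 8 patients in one arm respond.
- Uncorrected: 8/8 vs 4/7 gives χ² = 15·(8·3 − 0·4)² / (8·7·12·3) = 8640/2016 = 4.29, p = 0.038, so up to 4 of 7 responders is significant.
- Fisher: 4/7 gives p = 0.077 and 3/7 gives p = 0.026, so the limit is 3.
- Yates: 4/7 gives p = 0.155 and 2/7 gives p = 0.017; the limit is 2.

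If the true rates are 100% and 50%, power is P(Bin(7, 0.5) ≤ limit):
- Uncorrected: 99/128 = 77.3%.
- Fisher: 64/128 = 50.0%.
- Yates: 29/128 = 22.7%.

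With the 7-patient arm at 100%, the limits in the other arm are 4, 3 and 3 of 8. That gives 163/256 = 63.7%, 93/256 = 36.3% and 93/256 = 36.3%. All agree with the table.

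**Detectable difference.** If the better arm's rate is 80–95% (an assumption), 80% power needs a difference of 61–68 points (uncorrected), 66–70 (Fisher) or 75–78 (Yates). At a better-arm rate of exactly 100% the uncorrected test needs about 52 points if the larger arm is better, or 58 if the smaller is. These ranges depend on the rates chosen and are not a general property of the study.

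**Sensitivity to the assumptions.** Two departures pass 80% at 100% vs 50% with uncorrected chi-square:
- A 5:10 split with the larger arm at 100%: significant for up to 3 of 5, so P(Bin(5, 0.5) ≤ 3) = 26/32 = 81.2%.
- Two-sided 10% with the 7-patient arm at 100%: significant for up to 5 of 8, so P(Bin(8, 0.5) ≤ 5) = 219/256 = 85.5%. The test's actual size at that level is 12.2%.

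**Scale.** For an illustrative RUL–BL contrast of 60% vs 90%, 80% power needs about 31 (uncorrected) to 36 (Fisher) per arm.

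**The case against.** Several points on the other side are fair.

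- **The lack of a calculation is only missing detail.** That stands. The defect is that the text claims adequacy for an objective that its own numbers do not support.
- **Small studies are legitimate, and 15 ECT patients suffice for description.** That also stands. Objectives 1 and 3 are descriptive and can be carried out. The Analytical Plan starts with descriptive statistics and allows other procedures, so interval reporting is compatible with it. It is just not specified, and nothing labels RUL vs BL as a pilot or exploratory comparison.
- **The 30 may be meant as total enrolment including a reference group.** This is possible, since the controls have the same BFCRS measurements and Background gives them a purpose. A reader might infer that the 30 was derived for the wrong question, or that the controls are useless; the documents support neither. They show only that the controls cannot inform RUL vs BL, and that no listed objective compares ECT with no ECT.
- **The binary test is not the only analysis.** The plan also names t-tests and ANOVA. But the objective is worded as a response rate, and a t-test on BFCRS change with 7 vs 8 would itself need a difference of about 1.6 standard deviations for 80% power.
- **The wording is open-ended (30 or more).** The next sentence fixes the ECT group at 15.

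**Conclusion.** The point holds: the plan states an adequacy for RUL vs BL that its own design does not deliver. The mismatch between 30 enrolled and 15 informative patients follows from the text alone. The power figures rest on two-sided 5%, 7 vs 8 and no dropout. On those assumptions no 50-point difference reaches 80% power with any of the three tests, and a 30-point difference is missed about 65% of the time or more.

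A reader might go further and conclude that a 50-point difference can never reach 80% power, whatever the rates. The documents do not support that, because they fix neither the significance level nor the allocation ratio, and the two exceptions in the working exceed 80%. Both sit at the extreme pair of 100% vs 50%, and neither supports the adequacy statement.

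This should be fixed, because it affects what may be concluded from the likely non-significant result. It does not make the study unworkable.

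**What to change.** Replace the two Sample Size sentences with a statement covering these points:

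- 15 participants receive ECT and are randomised to RUL or BL, about 7–8 per arm if 1:1.
- This size is not powered for RUL vs BL, which is exploratory.
- Each response rate and the difference between them will be reported with exact or score 95% confidence intervals.
- A non-significant result will not be read as equivalence.

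In Background, reword the claim about comparing placements to match: the response rates will be described, and compared on an exploratory basis. Describe the 15 controls as a separate, non-randomised descriptive group.

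**Cost.** Wording in two sections and confidence intervals in the report, with no extra patients and no change to treatment. The downside is a less favourable stated claim. If the sponsor does intend an ECT-versus-control comparison, that is more than wording: it needs its own objective and a stated basis for 15 vs 15.

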- **Neurological conditions** – including TBI, seizure history, neurodevelopmental disorders, delirium, dementia

- The Montreal Cognitive Assessment (MOCA) will be administered the day prior to each ECT treatment and the day after each ECT treatment for pre and post procedure cognitive monitoring.

- **Incontinence**

- medical, metabolic, and/or psychiatric comorbidities are recorded but intentionally NOT excluded, with limited exceptions: CVA

- Questionnaires and rating scales: The following instruments will be administered by a trained clinician (psychiatric resident, medical student)

1) Bush- Francis Scale (BFCRS): The BFCRS is a rating scale consisting of 23 catatonia items (Bush et al., 1996a). The first 14 items on this scale are the most common, classical signs of catatonia & are also known as Catatonia Screening Instrument (BFCSI). If two or more of the BFCSI signs are present, for 24 hours or longer, catatonia is a possibility (Sienaert et al, 2011). For the purpose of this study, a score of 4 or more on the 23-item BFCRS will be considered for

inclusion in this study.

- 2) **Hamilton depression scale**
- 3) **Montreal Cognitive Assessment (MoCA)**

The administration of the BFCRS, Hamilton depression scale and MoCA will be completed before and after each ECT treatment.

- Labs and testing (to rule out organic causes of catatonia)

EEG electroencephalogram
EKG – electrocardiogram
CT scan of the head w/o contrast
CMP complete metabolic panel,
CBC diff complete blood count with differential
Thyroid studies TSH T3 T4
Metabolic/Inflammatory laboratory tests (in specific conditions)
Urine Analysis with Urine Drug Screen within 48 hours of admission)
Fe serum level
Fibrin D-dimer
–Magnesium (Mg)

- Pre-anesthesia work-up performed by the department of anesthesia to determine fitness for ECT. Anesthesia faculty will administer anesthesia to participants during the ECT procedure. They will monitor patient in the OR before, during and after the ECT procedure for at least 30 minutes for any adverse effects.
- ECT treatments will begin after initial evaluation as described above. ECT treatments will be administered three times a week.
- Participants will not be required to try and fail a challenge of IV or IM Lorazepam prior to being assigned to receive ECT treatments.

Setting

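### Nothing in the plan withholds RUL or BL placement from the person who scores the BFCRS, the only listed outcome of the only randomised comparison

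*Combined protocol and SAP*

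**What the plan says.** - **Randomisation (Design).** Consenting ECT patients are "randomly assigned to receive either bilateral electroconvulsive treatment (BLECT) or right unilateral electroconvulsive treatment (RULECT"). The control group is formed by refusal of ECT, so RUL versus BL is the only randomised comparison. Comparing their response rates is a stated objective.
- **Outcome (Outcome Measure(s)).** The only entry is "Reduction of 50% or more in the Bush- Francis Scale (BFCRS) score".
- **Same criterion, second use (Interventions and Interactions).** "These ECT treatments can be terminated earlier if study participants show objective clinical improvement defined as a reduction of 50% or more" on that scale.
- **Who rates.** The list of questionnaires and rating scales in Methods and Measures says "The following instruments will be administered by a trained clinician (psychiatric resident, medical student"). Interventions and Interactions says "Participants will be administered the Bush Francis Scale (BFCRS) by the principal investigator or the study coordinator".
- **When and where.** "The administration of the BFCRS, Hamilton depression scale and MoCA will be completed before and after each ECT treatment". Ratings take place in the patient's room on the ward, while "ECT treatments will be administered in OR at Wake Forest Baptist Health" (Setting).
- **Masking.** No section mentions blinding, an independent rater or concealment of placement. The study identifier on data forms (Confidentiality and Privacy) is a privacy measure. Videos appear in that section only as material to be deleted.

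**The concern.** The endpoint is a cut-off applied to a score that a clinician judges. A rater who knows the placement and expects more from one of the two could score that arm leniently. That would raise its response count. Because the same cut-off permits the course to end, it could also lower the recorded number of sessions. Randomisation does not protect against a difference that arises at measurement, and no later analysis can recover ratings that were made unmasked.

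The two descriptions of the rater are a separate matter of text. They need reconciling, but the conflict is not what causes the exposure to bias.

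**Working it through.** **1. Inputs from the documents.** There are 15 ECT patients and 15 controls, 30 in all (Sample Size). Entry requires a BFCRS of 4 or more, response is a fall of at least 50%, and there are up to 10 treatments. The documents give no response rate, rater error, RUL:BL split or time point at which response is counted.

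**2. Why one point matters.** At a baseline of 5, a later score of 3 is a 40% fall (no response) and a score of 2 is a 60% fall (response). One point decides the outcome.

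**3. Single post-treatment reading (all inputs assumed).** I simulated 400,000 patients per cell with identical arms.
- Baseline is a whole number, uniform over the range shown.
- The fractional decline is Beta(4m, 4(1−m)), with m tuned to give the unbiased response rate.
- The later reading has SD 1, is rounded, and cannot fall below 0.
- Response means a score of at most half of baseline.
- Every patient in one arm is then scored one point lower.

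Rise in response in the shifted arm, in percentage points:

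| Unbiased response | Baseline 4–8 | 6–12 | 4–16 | 8–20 |
|---|---|---|---|---|
| 40% | 22.7 | 16.4 | 16.0 | 11.2 |
| 50% | 21.6 | 16.0 | 15.5 | 11.1 |
| 60% | 19.4 | 14.8 | 14.1 | 10.4 |
| 75% | 14.2 | 11.0 | 10.6 | 8.0 |
| 90% | 6.7 | 5.3 | 5.3 | 4.0 |
| 95% | 3.6 | 2.9 | 2.9 | 2.2 |

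If only half of the arm is shifted, the rise is 5.2 to 9.7 points at 60% and 1.1 to 1.8 at 95%. A 2-point shift for all gives 19.3 to 32.0 points at 60% and 6.6 to 9.1 at 90%.

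**4. Response at any of 10 readings, with ECT ending there.** This assumes linear decline to session 10, a 1-point shift and 100,000 patients per cell. Ranges run over the same four baseline ranges.

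| Unbiased response | Rise in response (points) | Fewer recorded sessions (mean) |
|---|---|---|
| 60% | 11.6 to 25.4 | 0.8 to 2.5 |
| 75% | 8.6 to 17.8 | 0.9 to 2.4 |
| 90% | 4.3 to 7.9 | 1.0 to 2.2 |
| 95% | 2.3 to 4.1 | 0.9 to 2.0 |

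**5. Against sampling error.** Assume the 15 ECT patients split 7 and 8. One reclassified patient moves an arm by 1/8 = 12.5 or 1/7 = 14.3 points. The standard error of the difference is √[p(1−p)(1/7 + 1/8)]:
- 60%: √(0.24 × 0.2679) = 25.4 points
- 75%: √(0.1875 × 0.2679) = 22.4 points
- 90%: √(0.09 × 0.2679) = 15.5 points
- 95%: √(0.0475 × 0.2679) = 11.3 points

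**6. False-positive rate.** This is the exact probability of p < 0.05 from an uncorrected chi-square test, 7 versus 8, using the 1-point gains in step 3.

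| Unbiased response | No shift | Arm of 8 shifted | Arm of 7 shifted |
|---|---|---|---|
| 60% | 4.4% | 6.8–13.1% | 5.9–10.4% |
| 75% | 4.5% | 6.5–10.4% | 4.3–5.6% |
| 90% | 1.4% | 1.6–2.0% | 0.4–0.6% |
| 95% | 0.3% | 0.3% | 0.0–0.1% |

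**The case against.** **The plan is silent; it does not say that ratings are open.** It does not state who delivers ECT. Ward ratings and treatment in the operating room may already keep the rater apart from the procedure. This stands as a limit on the claim: the gap is a missing provision, not a demonstrated bias. Separate rooms alone, however, do not stop ward staff or notes from revealing placement.

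**The effect may be small.** The larger figures need low baselines and a lenient shift for every patient in one arm. The Background describes a very good record for ECT in catatonia, without giving a rate. If response is 90 to 95%, the single-reading gain is 2 to 7 points and the false-positive rate stays at 2% or less. The standard error exceeds the matching single-reading 1-point gain throughout 60 to 95%. All of this stands, and sample size limits the comparison more than rating does. But a standard error is reported alongside the estimate, whereas a rating bias stays hidden inside it. Nor do the documents support assuming a high response rate.

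**Masking may be hard to staff.** The principal investigator, one of the named raters, also has overall responsibility for data and safety monitoring, and adverse events are assessed for their relationship to ECT. That person may be difficult to keep unaware. The part played by residents and the coordinator in ECT is not described. This bears on which of the named staff should rate, not on whether placement should be withheld.

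**Conclusion.** The concern holds. A single judged threshold carries the only randomised comparison and can also end treatment, and no section withholds placement from its rater. The principal investigator or coordinator could follow the plan exactly and score it unmasked.

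The size depends wholly on assumed inputs. A uniform 1-point shift at one reading adds 10 to 19 points at 60% unbiased response, 8 to 14 at 75%, 4 to 7 at 90% and 2 to 4 at 95%. Shifting half the arm gives about 1 to 10 points over 60 to 95%. These are not upper bounds: lower response rates at baseline 4–8 give 22 to 23 points, and a 2-point shift gives up to 32. This should be corrected, with medium confidence that it would matter in practice. Masking would not make a comparison of about 7 versus 8 patients precise.

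**What to change.** 1. **Settle the rater.** Make Methods and Measures and Interventions and Interactions name the same group, drawn from the staff already listed in them and chosen with an eye to who can be kept unaware of placement.
2. **Add a masking statement**, for example: *The person who rates a patient's BFCRS, Hamilton and MoCA does not attend that patient's ECT and is not told whether it is RUL or BL; scores go to the treating team, and placement is not passed back to the rater.*
3. **State the limit.** The plan says "The control group will undergo all the same laboratory investigations and Bush Francis measurements", but ratings of ECT patients against this group, which refused ECT, cannot be masked in this way.

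**Cost.** No new assessments are needed, nor any new type of staff provided one of the named groups can be kept apart from ECT; the documents do not say. It puts a rota constraint on ratings already planned: at most 10 treatments × 2 × 3 scales = 60 per ECT patient, and 60 × 15 = 900 in all. The true load may be lower. On an assumed Monday, Wednesday and Friday schedule, the day after one treatment is often the day before the next. Ten treatments then give 14 rating days, so 14 × 3 = 42 ratings per patient and 42 × 15 = 630 in all if one rating serves both purposes. Placement must also be kept out of notes that the rater sees. Masking will be imperfect.

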Confidentiality will be protected by collecting only information needed to assess study outcomes, minimizing to the fullest extent possible the collection of any information that could directly identify subjects, and maintaining all study information in a secure manner. To help ensure subject privacy and confidentiality, only a unique study identifier will appear on the data collection form. Any collected patient identifying information corresponding to the unique study identifier will be maintained on a linkage file, stored separately from the data. The linkage file will be kept secure, with access limited to designated study personnel. Following data collection subject identifying information will be destroyed. Identifying data will be destroyed three years after closure of the study. Data stored on paper will be shredded and videos will be deleted. Data access will be limited to study staff. Data and records will be kept locked and secured, with any computer data password protected. All study procedures will take place in the participant's hospital room with study personnel. No one other than the participant and study personnel will be allowed in the participant's hospital room when any study procedure is underway. No reference to any individual participant will appear in reports, presentations, or publications that may arise from the study.

Data and Safety Monitoring

The principal investigator will be responsible for the overall monitoring of the data and safety of study participants. The principal investigator will be assisted by other members of the study staff.

Reporting of Unanticipated Problems, Adverse Events or Deviations

Any unanticipated problems, serious and unexpected adverse events, deviations or protocol changes will be promptly reported by the principal investigator or designated member of the research team to the IRB and sponsor or appropriate government agency if appropriate. Adverse Events will be collected and assessed for relationship for ECT treatments on ECT subjects only.

References

1. Kahlbaum KL. Die Katatonie: oder das Spannungsirresein, eine klinische Form psychischer Krankheit. 1973
2. World J Psychiatr. 2015 June 22; 5(2): 182-192.
3. Bush, G., Fink, M., Petrides, G., Dowling, F., Francis, A., 1996a. Catatonia. I. Rating scale and standardized examination. Acta Psychiatr. Scand. 93, 129–136.

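### Routine adverse-event collection appears limited to ECT subjects, so the 15 controls give no harm data to set beside theirs (low severity, cheap to fix)

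*Combined protocol and SAP*

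**What the plan says.** The section Reporting of Unanticipated Problems, Adverse Events or Deviations contains two rules.

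- Prompt reporting, with no limit by group: "Any unanticipated problems, serious and unexpected adverse events, deviations or protocol changes will be promptly reported".
- Routine collection: "Adverse Events will be collected and assessed for relationship for ECT treatments on ECT subjects only".

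Other places bear on the point:

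- **Background, Rationale and Context:** the control group is there to add information on early ECT treatment.
- **Design, on controls:** "The control group will undergo all the same laboratory investigations and Bush Francis measurements for evaluation of their catatonia but will not receive ECT". Adverse events are not mentioned. Controls are eligible patients who consent to the study but refuse ECT, or whose representative refuses it.
- **Design, on anaesthesia staff:** "They will monitor patient in the OR before, during and after the ECT procedure for at least 30 minutes for any adverse effects". This is tied to the ECT session.
- **Data and Safety Monitoring:** the principal investigator oversees the safety of all participants, but no collection procedure is given.
- **Sample Size:** 15 ECT subjects and 15 controls, 30 in total.
- **Interventions and Interactions:** "Participants will receive up to 10 ECT treatments", with early termination allowed on clinical improvement. BFCRS ratings fall "the day before each ECT procedure and the day after each ECT procedure". The Design section sets three treatments a week.
- **Outcome Measure(s) and Analytical Plan:** the only outcome is a BFCRS fall of at least 50%, and no safety analysis is named.

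**The concern.** The routine rule joins two different activities, recording an event and judging whether ECT caused it, and then restricts both to one group. Restricting the second makes sense, since relatedness to ECT has no meaning in someone not given ECT. Restricting the first makes harm ascertainment one-sided.

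These are inpatients whose comorbidities are mostly not grounds for exclusion, so some events would occur without ECT. OR monitoring, session-timed MoCA, timing within the patient and the RUL v BL contrast all help in interpreting an ECT subject's event. None of them shows how often common events arise in a similar admission without ECT. Only the controls could show that, and for routine events they contribute nothing. Events not recorded prospectively on a common form are hard to recover afterwards.

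**Working it through.** **1. The plan's own figure.** 15 + 15 = 30, which agrees with the stated total. The protocol gives no event rate, alpha or power, so nothing else can be reproduced.

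**2. Which control events are missed.** Setting the two rules side by side:

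| Event in a control | Prompt-reporting rule | Routine rule (natural reading) |
|---|---|---|
| Serious and unexpected, or an unanticipated problem | covered | not collected |
| Serious but expected | not covered | not collected |
| Non-serious | not covered | not collected |

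The last two rows are the gap. It applies to 15/30 = 50% of participants.

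**3. How many events that might be.** The per-patient risk p is an assumption. Expected controls with an uncollected event = 15p. The chance of at least one = 1 − (1 − p)^15.

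| p (assumed) | 15p | Chance of at least one |
|---|---|---|
| 10% | 1.5 | 79.4% |
| 20% | 3.0 | 96.5% |
| 30% | 4.5 | 99.5% |

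**4. A window from the protocol's own schedule.** Ten treatments have 9 intervals. At three a week, 9/3 = 3 weeks = 21 days, so the course runs from day 1 to day 22 if no session is missed. Adding the rating the day before the first treatment and the day after the last gives 22 + 2 = 24 days.

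**5. Why observation time must be common or reported.** A course stopped after 4 treatments (Monday, Wednesday, Friday, Monday) spans days 1 to 8, or 8 + 2 = 10 days with its ratings, against 24 for a full course. At one constant daily rate, a 20% risk over 24 days becomes 1 − (1 − 0.20)^(12/24) = 10.6% over 12 days. Unequal follow-up alone can therefore make groups look different.

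**6. What collection in controls would give.** Exact (Clopper-Pearson) 95% limits:

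- 0/15: upper limit 1 − 0.025^(1/15) = 21.8%.
- 3/15: 4.3% to 48.1%.
- For the ECT arms, with an assumed 8/7 split: 0/8 allows up to 36.9% and 0/7 up to 41.0%.

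For a formal ECT v control test (Fisher's exact, two-sided 0.05 assumed), significance needs at least 5/15 v 0/15, or 7/15 v 1/15. Power for an assumed 30% v 10% is 14.9%. The result can only be descriptive.

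**The case against.** The strongest reply is that this is a deliberate and proportionate choice. The study assigns controls no intervention, the events that matter most remain reportable in every group, and the principal investigator oversees everyone's safety. Safety is neither an objective nor an outcome. Most of this stands, and it is why the severity is low. It does not remove the gap, because general oversight is not a collection procedure, and serious but expected events in controls are also left out.

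A second reply is grammatical: the closing restriction could attach only to the assessment of relationship. That reading is possible. However, no other section sets up routine collection in controls, so the sentence would still need rewording to make the intention clear.

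A third reply is that control events would not be a clean background. That is right. The protocol names medication as an alternative to ECT and does not say what controls receive, so their events could include effects of other treatment as well as differences between refusers and acceptors.

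The following stronger readings are tempting, but the documents do not support them:

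- *Controls have no safety reporting at all.* The prompt-reporting rule carries no limit by group.
- *The trial's comparisons are compromised.* BFCRS is measured in controls too, and both RUL and BL subjects are inside routine collection.
- *The Confidentiality and Privacy section forbids collecting these events, because it says "Confidentiality will be protected by collecting only information needed to assess study outcomes".* Read that literally, it would also exclude the MoCA, Hamilton and laboratory data that the protocol plainly requires. It is general wording and is no obstacle.

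**Conclusion.** The point holds at low severity. On the natural reading of the routine rule, non-serious events and serious but expected events in 15 of 30 participants go uncollected. A control group meant to inform on early ECT then yields no harm data to set beside the ECT subjects' events.

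The only magnitude taken directly from the documents is the 15 of 30. Event rates, the 12-day stay, the 8/7 split and the test level are assumptions. The conclusion rests on the wording and on the absence of any other provision for controls, and it does not depend on those assumed values. Correcting it buys a rough description, confounded by refusal and concurrent treatment. It does not buy a powered comparison or a way to settle the cause of any single event.

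**What to change.** Replace the routine-collection sentence with:

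> Adverse events will be collected in all enrolled participants, on the same form, from the baseline rating to the end of a common observation window (up to 24 days, the span of the longest planned ECT course with its ratings) or discharge, whichever is earlier; relationship to ECT will be assessed in ECT subjects only.

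In the Analytical Plan, add that the number of participants with events and their observation time will be reported descriptively by RUL, BL and control, together with the treatments that controls received. State there that ECT v control is non-randomised, confounded by refusal and concurrent treatment, and imprecise.

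The cost is one replaced sentence, a short reporting statement, and event forms for 15 inpatients already being rated, plus some extra recording for ECT subjects who stop early. The downside is modest form-filling for a descriptive result. No separate rule for courses that overrun the window is needed, and the confidentiality wording can stay as it is.
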